11.4.2. Secondary Efficacy Endpoints

Secondary objectives are defined as follows:

- First occurrence of any RT-PCR-confirmed RSV disease
This is defined as new onset or worsening of any of the clinical symptoms (LRTI or upper respiratory tract infection [URTI]) indicated in [Attachment 1](#) in combination with RSV confirmation by RT-PCR in at least one of the samples taken at the visits after symptom onset (one positive sample is sufficient)
- First occurrence of a considered endpoint is defined as the first episode of the considered endpoint in a given RSV season (regardless A or B strain, unless otherwise specified).

11.4.2.1. Analysis

For each of the above secondary endpoints an exact Poisson regression will be fitted in a similar way as for the primary endpoint. The 95% 2-sided CI for the VE (1-relative risk rate) will be calculated from the regression model described above.

In addition, for each of the above secondary endpoints, the proportion of participants with an event will be tabulated. The corresponding VE (1- relative risk) and the 95% 2-sided CI will be calculated without taking the strata into account based on an exact binomial test.

11.4.3. Exploratory Efficacy Endpoints

- Explore the relationship between G-ELISA and RT-PCR confirmed RSV infection.
Provided a cut-off for G-ELISA fold-rise between ARI Day 3-5 and ARI Day 29 is found that is sufficiently sensitive and specific for serology confirmation of RSV infection, the following objectives will be explored:

First occurrence of any serology and/or RT-PCR-confirmed RSV disease

This is defined as new onset or worsening of any of the clinical symptoms (LRTI or URTI) indicated in [Attachment 1](#) in combination with RSV confirmation by RT-PCR in at least one of the samples taken at the visits after symptom onset (one positive sample is sufficient) or serology confirmation of RSV

First occurrence of serology-confirmed RSV-mediated LRTD according to each case definition

This is determined in a similar way as the primary endpoints but instead of RT-PCR confirmation of RSV, serology confirmation of RSV is needed. Serology confirmation is determined based on the serology sample obtained approximately 28 days after ARI onset.

First occurrence of any serology-confirmed RSV disease

This is defined as new onset or worsening of any of the clinical symptoms (LRTI or URTI) indicated in [Attachment 1](#) in combination with serology confirmation of RSV

- If the primary objective is demonstrated after one RSV season:

First occurrence of RT-PCR-confirmed RSV-mediated LRTD during the second RSV season and during the third RSV season according to each of the 3 case definitions

This is defined similarly as the primary endpoint, but only counted in the respective season. The baseline assessment for the second RSV season is the Day 365 (Month 12) visit and for the third RSV season it is the Day 730 (Month 24) visit. New onset or worsening is defined similarly as for the primary endpoint, by comparing symptoms occurring during the ARI episode to symptoms reported at the new baseline (instead of by comparing to Day 1). First occurrence of a considered endpoint during the second or third RSV season is defined as the first episode of the considered endpoint in a given RSV season (regardless A or B strain, unless otherwise specified).

First occurrence of RT-PCR-confirmed RSV-mediated LRTD over 2 RSV seasons and over 3 RSV seasons according to each of the 3 case definitions

This is defined similarly as the primary endpoint but taking into account events over the 2 or 3 seasons. The baseline assessment for the second RSV season is the Day 365 (Month 12) visit and for the third RSV season it is the Day 730 (Month 24) visit. New onset or worsening is defined similarly as for the primary endpoint, by comparing symptoms occurring during the ARI episode to symptoms reported at the new baseline (instead of comparing to Day 1). When evaluating the vaccine efficacy over 2 and 3 seasons, first occurrence of a considered endpoint over 2 or 3 seasons is defined as the first episode of the considered over the considered period (2 RSV seasons or 3 RSV seasons respectively, regardless A or B strain, unless otherwise specified).

Other secondary or exploratory objectives that were assessed during the first RSV season (as defined in section 11.4.2 and below), might also be explored during the second and the third RSV season and over 2 and 3 RSV seasons. These endpoints are defined similarly as the corresponding endpoints during the first RSV season, but baseline, new onset or worsening, and first occurrence are defined in a similar way as for RT-PCR-confirmed RSV-mediated LRTD, during the second and the third RSV season and over 2 or 3 RSV seasons (see above).

- First occurrence of any RT-PCR-confirmed RSV disease caused by an RSV A or RSV B strain, respectively
- First occurrence of potential complications of respiratory disease (eg, pneumonia, new onset, worsening, or an exacerbation of CHF, asthma, and COPD) linked to any respiratory disease and linked to any RT-PCR confirmed RSV disease
- Efficacy of active study vaccine against other respiratory diseases
Midturbinate nasal swabs may be tested for the presence of other respiratory pathogens
- First occurrence of hospitalization linked to any respiratory disease and linked to any RT-PCR confirmed RSV disease
- Determination of oxygen saturation during clinical assessment during ARI episodes
- First occurrence of RT-PCR-confirmed RSV-mediated LRTD according an ordinal case definition

The ordinal case definitions are provided in [Table 12](#).

Table 12: Ordinal Case Definition

Ordinal Case definition	Ordinal variable	Participants fulfilling
≥3 symptoms of LRTI (new onset or worsening), in combination with confirmation of RSV by RT-PCR in one or more of the midturbinate nasal swabs, or in the sputum sample (when available)	4	Case Definition 1, 2 and 3
2 symptoms of LRTI (new onset or worsening), in combination with confirmation of RSV by RT-PCR in one or more of the midturbinate nasal swabs, or in the sputum sample (when available)	3	Case Definition 2 and 3 (not Case definition 1)
1 symptom of LRTI (new onset or worsening), in combination with confirmation of RSV by RT-PCR in one or more of the midturbinate nasal swabs, or in the sputum sample (when available)	2	Only Case Definition 3 (not Case definitions 1 and 2)
Other	1	No case definition

The CEC review will assess, independently and based on CRF/eDiary data, the location of the ARI (upper or lower respiratory tract infection) and the ARI severity. The CEC assessment, as well as other information based on MRU, presence of clinically relevant disease, use of therapeutic interventions, RiiQ, clinical assessment, Lawton-Brody IADL, and change in frailty will be used to evaluate the severity of the RSV-positive ARIs, and will be used to explore the relation with the case definitions.

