11.4. Efficacy Analyses

11.4.1. Primary Efficacy Endpoints

Three primary efficacy endpoints are defined as follows:

- First occurrence of RT-PCR-confirmed RSV-mediated LRTD according to Case Definition #1
- First occurrence of RT-PCR-confirmed RSV-mediated LRTD according to Case Definition #2
- First occurrence of RT-PCR-confirmed RSV-mediated LRTD according to Case Definition #3

The case definitions are defined as follows:

Case Definition #1	Case Definition #2	Case Definition #3
≥3 symptoms of LRTI (new onset or worsening)	≥2 symptoms of LRTI (new onset or worsening)	≥2 symptoms of LRTI, OR ≥1 symptom of LRTI combined with ≥1 systemic symptom
		(new onset or worsening)

LRTI = lower respiratory tract infection

To meet the primary endpoint according to the respective case definitions the following criteria will be taken into account:

- symptoms reported by participants on the RiiQ Symptom Scale and body temperature during the full ARI episode OR
- clinical assessment terms reported by a qualified study staff member during the ARI Days 3-5 clinical visit

in combination with

- confirmation of RSV by RT-PCR in one or more of the midturbinate nasal swabs, or in the sputum sample (when available)

Of note, on the day of the ARI Days 3-5 clinical visit, the case definitions can be met by symptoms reported by participants on the RiiQ or by signs and symptoms reported by the qualified study staff member. Case definitions cannot be met by a combination of symptoms reported by the participant with signs and symptoms reported by the qualified study staff member.

Confirmation of RSV infection by RT-PCR (midturbinate swabs and sputum sample, when available) will be performed at the central laboratory. For participants hospitalized with symptoms of an ARI, confirmation of RSV infection using an FDA-approved RT-PCR test at the local (hospital) laboratory will also be used for the analysis of case definitions if results from the central laboratory are not available. One positive sample (defined as any sample with a value above the limit of detection) is sufficient.

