As a sensitivity analysis, the analysis of the primary endpoint will be repeated, but participants with RSV infection and a co-infection with at least one other respiratory virus (ie, confirmed using an FDA approved RT-PCR test in one or more of the midturbinate nasal swabs, or in the sputum sample, when available) will not be considered as a case for that episode, as the etiology of the symptoms will be indeterminate.

As an additional sensitivity analysis, the analysis of the primary endpoint will be repeated, taking into account only the RT-PCR test results from the central laboratory (ie, excluding the local test results for hospitalized participants).

Presence and severity of symptoms will be collected using participant responses to the RiiQ Symptom Scale and temperature readings participants report in the eDiary each day throughout each ARI episode. On the day of the ARI Days 3-5 clinical visit, signs and symptoms will also be collected by qualified study staff in a clinical assessment.

Table 11: Symptoms of Lower Respiratory Tract Infection and Systemic Symptoms as per RiiQ or Clinical Assessment

	Symptoms from Case Definition	RiiQ Term	Clinical Assessment Term (ARI Days 3-5 Clinical Visit)
Symptoms of LRTI	Cough	Cough	Cough
	Shortness of breath	Short of breath	Dyspnea or decreased oxygen saturation*
	Sputum production	Coughing up phlegm (sputum)	Sputum production
	Wheezing	Wheezing	Wheezing; rhonchi, rales or other sign of consolidation
Systemic Symptoms	Tachypnea**		Tachypnea
	Fatigue	Fatigue (tiredness)	Malaise (tiredness)
	Fever***,****		Fever
	Feverishness****	Feeling feverish	

* Decreased oxygen saturation is defined as oxygen saturation of <90% for participants with a baseline oxygen saturation of $\geq 90\%$ at randomization; for participants with baseline oxygen saturation <90%, decreased oxygen saturation is defined as a $\geq 3\%$ decrease in their oxygen saturation from baseline.

** Tachypnea is defined as respiratory rate >20 breaths per minute.

*** Fever (ie, temperature >37.8°C) will be reported via daily temperature measurement and during ARI Days 3-5 clinical visit.

**** Feeling feverish and fever are considered as 1 symptom.

LRTI =lower respiratory tract infection, RiiQ = Respiratory Infection Intensity and Impact Questionnaire

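### Table 12 gives two different ordinal levels to an RSV-positive episode with exactly one LRTI symptom and no systemic symptom

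*Protocol*

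**What the plan says.** Section 11.4.3 lists among the exploratory endpoints "First occurrence of RT-PCR-confirmed RSV-mediated LRTD according an ordinal case definition" and refers to Table 12 for the scale. The table has three columns: a symptom rule, the ordinal value, and the case definitions that participants at that level fulfil.

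- Level 4: three or more LRTI symptoms; fulfils Case Definitions 1, 2 and 3.
- Level 3: two LRTI symptoms; fulfils 2 and 3 but not 1.
- Level 2: "1 symptom of LRTI (new onset or worsening), in combination with confirmation of RSV by RT-PCR"; labelled "Only Case Definition 3 (not Case definitions 1 and 2" in the third column.
- Level 1: everything else; labelled "No case definition".

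Section 11.4.1 defines Case Definition #3 by two routes: at least two LRTI symptoms, or "≥1 symptom of LRTI combined with ≥1 systemic symptom". The synopsis gives the same definition. Table 11, titled "Symptoms of Lower Respiratory Tract Infection and Systemic Symptoms as per RiiQ or Clinical Assessment", lists fatigue or malaise and fever or feverishness as systemic symptoms, in a class apart from the LRTI symptoms.

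**The concern.** The level 2 row states two rules that are not equivalent. Its symptom column omits the requirement of "≥1 systemic symptom", which Case Definition #3 imposes when there is only one LRTI symptom. Its label column says that the row contains Case Definition #3 cases. An episode with one LRTI symptom and nothing systemic satisfies the first rule and fails the second.

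Such episodes can enter the database. Attachment 1 defines an ARI by a single respiratory symptom, so surveillance picks up an illness consisting of cough alone. The secondary endpoint in Section 11.4.2 already counts RT-PCR-confirmed RSV disease with any single upper or lower respiratory symptom. The protocol therefore recognises RSV illness that is not LRTD under any of the three definitions, and the symptom column of Table 12 blurs that boundary.

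At stake is whether the ordinal scale maps onto the three case definitions, as its third column says it does. Section 1.2 gives choosing a case definition for Phase 3 as a reason for testing all three. A level 2 that mixes Case Definition #3 cases with non-cases is less useful for that purpose.

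**Working it through.** No sample size, power or alpha figure is involved, so there is no stated number to reproduce. The check is one of logic.

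**Inputs.** Let *L* be the number of LRTI symptoms and *S* the number of systemic symptoms in an RSV RT-PCR-positive episode, counting only symptoms that qualify under Section 11.4.1.

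- Case Definition #1: *L* ≥ 3.
- Case Definition #2: *L* ≥ 2.
- Case Definition #3: *L* ≥ 2, or (*L* ≥ 1 and *S* ≥ 1).
- Symptom column of Table 12: level 4 if *L* ≥ 3, level 3 if *L* = 2, level 2 if *L* = 1, otherwise level 1.
- Case-definition column: level 4 if #1 is met; level 3 if #2 but not #1; level 2 if #3 only; level 1 if none.

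**Enumeration.** Taking *L* from 0 to 5 and *S* from 0 to 2 gives 6 × 3 = 18 combinations.

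| *L* | *S* | Definitions met | Level by symptom column | Level by case-definition column |
|---|---|---|---|---|
| 0 | 0, 1, 2 | none | 1 | 1 |
| 1 | 0 | none | **2** | **1** |
| 1 | 1, 2 | #3 only | 2 | 2 |
| 2 | 0, 1, 2 | #2, #3 | 3 | 3 |
| 3, 4, 5 | 0, 1, 2 | #1, #2, #3 | 4 | 4 |

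The columns agree in 17 combinations and disagree in one: *L* = 1, *S* = 0. The upper limits chosen for *L* and *S* do not matter, because the rules do not change beyond *L* = 3 or *S* = 1.

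**Effect on the counts.** By the symptom column, levels 2 to 4 together hold every RSV-positive episode with *L* ≥ 1. Case Definition #3 holds those with *L* ≥ 2, plus those with *L* = 1 and *S* ≥ 1. The difference is exactly the number of episodes with *L* = 1 and *S* = 0. Levels 2 to 4 therefore sum to the Case Definition #3 count only if there are no such episodes. Levels 3 and 4 are the same under either column.

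**After correction.** If level 2 also requires *S* ≥ 1, the combination *L* = 1, *S* = 0 falls to level 1 and the columns agree in all 18 combinations.

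**The case against.** The strongest reply is that little depends on this row. The ordinal endpoint is one bullet among the exploratory endpoints and does not appear in the objectives and endpoints table of Section 2.1. It carries no hypothesis, no alpha and no decision rule. The 14-event and 18-event triggers, the superiority and futility assessments and proof of concept all use the three primary case definitions, which are stated consistently. That stands, and it sets the grade of the point.

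A second reply is that the table shows which reading is meant: the third column defines levels by case definition, and Case Definition #3 is spelled out in Section 11.4.1. That makes one reading more likely. It does not remove the conflict, because no footnote or other text says which column governs, and the symptom column by itself is a coherent count scale. Section 11 leaves specific details to the SAP, which is not among the documents reviewed. A SAP could choose a column, but it cannot follow both.

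Three stronger readings are tempting, and the documents do not support them.

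- A reader might infer that every one-symptom episode is misclassified. Episodes with one LRTI symptom plus fatigue or fever are level 2 by both columns.
- A reader might infer that a treatment comparison of severity shift is compromised. The protocol specifies no ordinal shift analysis: Section 11.4.3.1 gives a Poisson model for endpoints that explore VE and tabulation for categorical endpoints.
- A reader might size the error from the worked example in Section 11.4.1.1 (14, 18 and 25 events for Definitions 1, 2 and 3). There, 25 − 18 = 7 events would be level 2, so each misfiled episode would add 1/7, about 14%. Those counts are a hypothetical illustration of alpha splitting, not a forecast of the case mix.

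**Conclusion.** Table 12 contradicts itself for RSV-positive episodes with exactly one LRTI symptom and no systemic symptom: level 2 by the symptom column, level 1 by the case-definition column. Followed literally, the symptom column counts episodes that meet no case definition as level 2 of an LRTD endpoint.

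The conclusion rests only on the wording of Table 12 and of Case Definition #3. The level 2 row is complete and parallel to the rows above it, so text lost in extraction is an unlikely explanation. The number of episodes affected is not stated and cannot be derived from the protocol.

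Severity is minor. The effect is confined to the counts at levels 1 and 2 of one exploratory endpoint and anything derived from them. Inflation of a primary, secondary or interim result is not supported.

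**What to change.** Reconcile the two columns of Table 12. The preferred edit is to make the level 2 row require one LRTI symptom together with at least one systemic symptom, each new or worsened, plus RT-PCR confirmation. One-symptom episodes without a systemic symptom then fall to Other (level 1). This matches the third column and the endpoint's name, and it makes levels 2 to 4 sum to the Case Definition #3 count.

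If a pure count of LRTI symptoms was intended, keep the symptom column and correct the third-column labels for levels 2 and 1. Those labels should show that level 2 may include episodes meeting no case definition, and that level 1 does not hold all such episodes.

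Either choice costs a line or two in Table 12 and the matching change in the derivation specification. It needs no new data and no change to the sample size, alpha allocation or event triggers.

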11.4.3.1. Analysis

For endpoints that intend to explore VE, an exact Poisson regression model will be fitted in a similar way as for the primary endpoint. The 95% 2-sided CI for the VE (1-relative risk rate) will be calculated from the regression model described above.

For exploratory endpoints regarding only season 2 data, the follow-up time for cases in season 2 is defined as the time between the Day 365 (Month 12) visit and the occurrence of the first event (according to the considered endpoint) in the considered season, for non-cases in season 2, it is the time between the Day 365 visit and the end of the second season visit. However, for participants that discontinued before the end of the second season and had an event in Season 2 (according to the considered endpoint), the follow-up time is defined as the time between the Day 365 visit and the occurrence of the first event and for participants that discontinued before having an event in season 2, follow-up time is the time between the Day 365 visit and the date of last contact. Participants that discontinued prior to the Day 365 visit as well as participants that are part of Revaccination Subcohort A will be excluded from the analysis.

For exploratory endpoints regarding only Season 3 data, the follow-up time for cases in Season 3 is defined as the time between the Day 730 (Month 24) visit and the occurrence of the first event (according to the considered endpoint) in the considered season, for non-cases in Season 3, it is the time between the Day 730 visit and the end of the third season visit. However, for participants that discontinued before the end of the third season and had an event in Season 3 (according to the

considered endpoint), the follow-up time is defined as the time between the Day 730 visit and the occurrence of the first event and for participants that discontinued before having an event in Season 3, follow-up time is the time between the Day 730 visit and the date of last contact. Participants that discontinued prior to the Day 730 visit as well as participants that are part of Revaccination Subcohorts A and B will be excluded from the analysis.

For exploratory endpoints over 2 seasons (Season 1 and Season 2), the follow-up time is defined as the time between the Day 1 vaccination and the occurrence of the first event (according to the considered endpoint) in the first 2 seasons, for non-cases, it is the time between the Day 1 vaccination and the end of the second season visit. However, for participants that discontinued before the end of the second season and had an event (according to the considered endpoint), the follow-up time is defined as the time between the Day 1 vaccination and the occurrence of the first event and for participants that discontinued before having an event, follow-up time is the time between the Day 1 vaccination and the date of last contact. For Revaccination Subcohort A participants, only the first season is taken into account: for cases during the first season, the follow-up time is the time between the Day 1 vaccination and the occurrence of the first event (according to the considered endpoint), for non-cases it is the time between the Day 1 vaccination and end of first season visit.

For exploratory endpoints over 3 seasons (Season 1, 2 and 3), the follow-up time is defined similar as for endpoints over 2 seasons, but data up to the end of the third season are taken into account (instead only data up to the end of the second RSV season). For Revaccination Subcohort A participants, only the first season is taken into account and follow-up time is defined similar as explained above. For Revaccination Subcohort B participants only the first 2 seasons are taken into account: for cases during the first 2 seasons, the follow-up time is the time between the Day 1 vaccination and the occurrence of the first event (according to the considered endpoint), for non-cases it is the time between the Day 1 vaccination and the end of second season visit.

For continuous endpoints, actual values and changes from baseline (if meaningful) will be summarized descriptively. Categorical endpoints will be tabulated.

11.5. Patient-reported Outcomes

Daily symptom severity reported by participants using the RiiQ Symptom Scale, temperature log, and Patient Global Impression Scales from symptom onset to symptom resolution will be descriptively analyzed by group (active vaccine or placebo). Changes from baseline functioning associated with ARI collected using the RiiQ Impact Scales will also be analyzed.

Details on validation of the PRO questionnaires will be provided in a separate analysis plan.

11.5.1. Respiratory Infection Intensity and Impact Questionnaire (RiiQ™v2)

The RiiQ consists of 4 scales that are scored separately:

- RiiQ Symptom Scale (Question 1). Each symptom is rated on the following scale: 0 None, 1 Mild, 2 Moderate, and 3 Severe. The RiiQ Symptom scale can be scored as a mean of all

scores (Total Symptom Score) or 2 subscales scores, Respiratory Symptoms and Systemic Symptoms:

The RiiQ Respiratory Symptoms Subscale score is the mean of 6 symptoms, ie, 2 URTI symptoms (Nasal congestion and Sore throat) and 4 LRTI symptoms (Cough, Wheezing, Shortness of breath, and Coughing up phlegm/sputum)

The RiiQ Systemic Symptom subscale score is the mean of 7 systemic symptoms (Headache, Feeling feverish, Neck pain, Body aches and pain, Fatigue/tiredness, Interrupted sleep, and Loss of appetite).

- RiiQ Impact Scales (Questions 2 to 4):

RiiQ Impact on Daily Activity scale (Question 2) consists of 7 activities. Ability to perform each activity item is rated on the following scale: 0 No difficulty, 1 Some difficulty, 2 Moderate Difficulty, and 3 Great difficulty. Scale scores are calculated as the mean of all 7 items (range 0-3).

RiiQ Impact on Emotions scale (Question 3) consists of rating 4 negative emotions, rated on the following scale: 0 Not at all, 1 Somewhat, 2 Moderately, and 3 Extremely. Scale scores are calculated as the mean of all 4 items (range 0-3).

RiiQ Impact on Relationships scale (Question 4) consists of 5 problems that a respiratory infection may cause in relationships with others, rated on the following scale: 0 Not at all concerned, 1 Somewhat concerned, 2 Moderately concerned, and 3 Extremely concerned) with scale scores calculated as the mean of all 5 items (range 0-3).

